1.2 Primary Study Endpoints

- Change in Overall SPADI scores at baseline compared to 2,4, and 6 months.
- Adverse reactions to the steroid

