2.0 Background

2.1 Scientific Background and Gaps

Osteoarthritis (OA) affects 54.4 million US adults and 23.7 million (43.5%) have arthritis-attributable activity limitation¹. As the condition progresses, pain and functional disability increase. Patients usually begin treatment with conservative measures including physical therapy and administration of nonsteroidal anti-inflammatory drugs before obtaining a corticosteroid injection². Corticosteroid injections have a patient-specific duration that often provide relief for a month before the effects begin to taper with most individuals returning to baseline by 2-3 months post injection^{3,4}.

Unfortunately, data on intraarticular injections is not robust and primarily focused on hip, knee, and disease processes rather than the glenohumeral joint⁶⁻⁸. For example, steroid concentrations have been studied in adhesive capsulitis, where 20 and 40mg of triamcinolone acetonide were used with no statistical significance between the two⁶. When a placebo was added, both doses were better than the placebo, but once again no difference was seen between the two steroid concentrations⁷. Another study, looking at knee osteoarthritis, found that high dose steroids had a larger effect on duration⁸, but other studies have shown no difference in duration between the 40mg and 80mg concentration of triamcinolone acetonide⁹.

Intraarticular injections do have adverse effects. Similar to steroids taken orally or intravenously, intraarticular injections have a similar side effect profile. Fortunately, intraarticular injections are localized, by the nature of the procedure, and the chances of experiencing a significant side effect is rare^{10,11}. The most common side effects are steroid flare, allergic reaction, facial erythema, hypo- pigmentation, fat pad necrosis, cutaneous atrophy, and a transient increase in blood glucose¹¹. Some of the rare side effects have been seen in case reports include idiopathic central serous chorioretinopathy, decrease in breast milk production, sepsis, tendon rupture, and cataracts¹¹. In addition, the administration of steroid injections are limited to being done every three months due to risk of weakening tendons, and acceleration of cartilage loss^{11,12}.

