7.2.3 Post-Clinic appointment

Patients will be contacted via telephone at 2 weeks to determine if any significant adverse outcomes have occurred. Patients will be contacted at 2 months, 4 months, and 6 months following the injection by email and/or phone call for completion of the SPADI and assessment of any adverse events that may have occurred as a result of the injection. Patients will also be asked what, if any, pain medications have been used in the month prior to the phone call. Patients will be given the option to complete the SPADI using the REDCap system or on paper. Patients wishing to complete the survey online will be emailed a link to access REDCap. A paper version of the survey will be mailed to the patient if that is their preferred method. A self-addressed stamped envelope will be included with the mailings. If the patient perceives that they have experienced an adverse effect the research coordinator will make a detailed record of the patient experience and the PI of the study will be contacted. .

At 12 months following the initial injection, in addition to a chart review, the patient will be contacted to determine the outcome of their shoulder pain and determine if the patient underwent any additional procedures and/or surgeries to the shoulder.

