10.3 Method of collection of safety information

Safety information will be collected by phone interview during the follow up phone calls as well as review of the electronic medical record.

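### Adverse reactions are a primary endpoint, but the only contact before 2 months asks about undefined significant outcomes, so the milder listed reactions are likely to be under-ascertained

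*Combined protocol and SAP*

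**What the plan says.** Section 1.2 lists "Adverse reactions to the steroid" as a primary endpoint beside the change in SPADI. Section 1.1 makes side effects part of both the purpose and the hypothesis. No definition, grading, time window or summary measure is given for this endpoint. Section 8.3 does not name it; the generic Fisher's exact test for categorical variables is the only test that would apply.

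Section 2.1 states which reactions are expected: "The most common side effects are steroid flare, allergic reaction, facial erythema", followed by several skin and fat-pad changes and a passing rise in blood glucose. The same section describes a significant side effect as rare. Section 11.0 adds pain and swelling at the injection site, and infection.

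Collection is set out in 7.2.3 and Section 10:
- **2 weeks:** "Patients will be contacted via telephone at 2 weeks to determine if any significant adverse outcomes have occurred".
- **2, 4 and 6 months, by email and/or phone:** "assessment of any adverse events that may have occurred as a result of the injection".
- **Trigger for a detailed record by the research coordinator:** "If the patient perceives that they have experienced an adverse effect".
- **Sources (10.3):** "Safety information will be collected by phone interview during the follow up phone calls as well as review of the electronic medical record".
- **Timing (10.4):** events are to be collected as they occur. No route for reporting between contacts is described.

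**The concern.** The contact closest to the injection is the best chance to learn about flare, flushing or a short glucose rise. At that contact the question is restricted to *significant* outcomes, the class that 2.1 calls rare. A caller who follows the text need not ask about the milder reactions that 2.1 calls most common.

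The next question comes about two months after the injection. It is open, names no reactions, and covers only events resulting from the injection. The patient must therefore remember a possibly brief event and also attribute it to the injection. Medical record review will mainly find events that led to care, so a mild reaction managed at home is unlikely to appear there.

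What is at stake is the safety half of the hypothesis. If many mild reactions are missed, a comparison showing no difference between doses could be read as evidence that the doses have similar side effects, when the reactions were not asked about in time.

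**Working it through.** **1. The plan's own figures.** The documents give no rate, power or sample size for adverse reactions. The group size comes from the SPADI calculation in 8.2: margin 15, assumed difference 4, SD 20, one-sided 2.5%, power 80%.

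n = 2 × (1.960 + 0.842)² × 20² / (15 − 4)² = 2 × 7.85 × 400 / 121 ≈ 51.9, so 52 per group, as stated. Dividing by 0.9 for 10% loss gives 57.8. The plan uses 57, hence 171 in total. I use 57 per arm as enrolled and 52 per arm as the analysable number after the planned loss.

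**2. Assumptions (not in the documents).** True reaction rates of 10%, 20% and 30% at 20, 40 and 80 mg, and a capture fraction c that is the same in every arm. The test is the exact 3×2 Fisher test at 5%, with power obtained by full enumeration.

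**3. Effect on the difference.** The observed rate in each arm is c × p, so the observed 20 mg vs 80 mg difference is c × (30% − 10%): 20 points at c = 1, 15 at c = 0.75 and 10 at c = 0.5.

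**4. Effect on power, three groups.**

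| Capture | Observed rates | Power, 57 per arm | Power, 52 per arm |
|---|---|---|---|
| 100% | 10 / 20 / 30% | 67% | 62% |
| 75% | 7.5 / 15 / 22.5% | 50% | 46% |
| 50% | 5 / 10 / 15% | 33% | 30% |

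If the true rates were 5%, 10% and 15%, power at 57 per arm would be 33% at full capture and 14% at half.

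**5. Cross-check, 20 mg vs 80 mg only (two-sided Fisher, 57 per arm, assumed rates).**

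| True rates | Capture 100% | 75% | 50% |
|---|---|---|---|
| 5% vs 20% | 59% | 41% | 21% |
| 10% vs 30% | 71% | 52% | 30% |
| 15% vs 40% | 82% | 63% | 39% |

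Halving capture costs about 40 percentage points in each row.

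**6. The opposite error.** A checklist can also collect yes answers that have nothing to do with the injection. If a fraction b in every arm answers yes for an unrelated reason, the observed rate is 1 − (1 − p)(1 − b). With p = 10/20/30% and 57 per arm:
- b = 10% gives 19 / 28 / 37% and power of about 46%.
- b = 20% gives 28 / 36 / 44% and power of about 33%.

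An any-yes composite could thus lose as much power as missing half the reactions. This shapes the fix below.

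**The case against.** The plan does more than the 2-week call. At 2, 4 and 6 months it asks about any adverse events, with no severity filter and with reach back to the injection. Section 10.1 describes an adverse event log, 10.3 adds record review, and 10.4 says events are collected as they occur. All of this stands and narrows the gap. It does not close it: the unfiltered question is late and open, and no reporting route between contacts is described.

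Four stronger readings are tempting, and the documents do not support them:
- **That a record is made only if the patient perceives an adverse effect.** Section 7.2.3 ties a *detailed* record and contact with the principal investigator to perception. It does not say that nothing else is recorded.
- **That reactions are in fact under-counted.** The documents give no rates and no capture fraction. What they support is a likely risk of unknown size.
- **That mild reactions carry most of the dose information, or are all short-lived.** No section relates any reaction to dose, and 2.1 calls only the glucose rise transient. A reaction still present at 2 months would fall within the unfiltered question.
- **That the bias must run towards equality.** That holds if capture is the same in each arm. Unequal capture could distort the comparison in either direction.

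It is also fair to object that a checklist has its own cost. These patients already have a painful shoulder, so a composite counting any pain would add unrelated positives, as step 6 shows.

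**Conclusion.** The point holds as a weakness in how a primary endpoint is ascertained. The one scheduled contact before 2 months filters on an undefined word, and the listed reactions are never asked about in a structured way close to the injection. Under-ascertainment of the milder reactions is likely.

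Its size cannot be computed from the documents. The illustration, a fall in power from about 67% to 50% or 33% at 57 per arm (62% to 46% or 30% at 52), rests on assumed rates, assumed capture of 75% or 50%, equal capture across arms and no background positives. The case for changing the 2-week question does not depend on those figures. The change should be in place before the 2-week calls are made, because events missed then cannot be reliably recovered later.

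**What to change.** **In 7.2.3:**
- Delete *significant* from the 2-week question.
- At 2 weeks, ask every patient, in the same words, a short yes/no list of the reactions named in 2.1 and 11.0, with onset and duration for each yes.
- Repeat the list at 2, 4 and 6 months for new events since the last contact.

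**In 1.2 and 8.3:**
- Report each reaction by arm.
- Define the primary safety comparison as the proportion of patients with a listed reaction of new onset or worsening after the injection, by 2 weeks, and name the test.
- Count injection-site pain only if it is new or worse than before the injection. Section 7.2.2 already elicits pain levels before and after the injection.
- Report self-monitored glucose rises separately, with the number of patients who monitor as the denominator. Section 7.2.2 does not record who monitors, so the form must ask.

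**Cost:** a one-page form, a few minutes per call, more minor events recorded, and some background positives that the new-or-worse rule limits but does not remove. No added visits, tests or staff.

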7.3 Duration of Participation

Patients will be followed for 1 year following the injection

8.0 Subject Numbers and Statistical Plan

8.1 Number of Subjects

Total number of subjects will be 171 allowing for 10% loss to follow-up.

8.2 Sample size determination

This is a three arm trial comparing three different doses of steroid (20mg, 40mg, 80mg) in patients with glenohumeral arthritis. The primary endpoint is change in overall pain score on the SPADI at two, four, and six months from baseline. The sample size is determined based on assuming a minimal clinically meaningful difference in the 20mg vs 80mg groups as well as conducting non-inferiority tests in the 20mg vs 40mg and 40mg vs 80mg groups. Let d_1 , d_2 , and d_3 be the average change in overall pain scale for the three different doses (low, medium, high). For the first part, in the 20mg vs 80mg groups, we wish to have sufficient statistical power based on the assumption of a moderate Cohen effect size of .5 (e.g. differences of 40 vs 20 with a standard deviation of 40). This requires a sample size 51 per group based on a two-sided 80%-power 5%-level t-test. For the non-inferiority test, we assume d_1 , d_2 , and d_3 are 40, 36, and 32 (so $d_3-d_2=d_2-d_1=4$) with a standard deviation of 20. Allowing for a non-inferiority margin of 15 (so that differences less than 15 are deemed clinically non-inferior), a sample size of 52 per group based on an 80%-power 2.5%-level (since there are two tests) non-inferiority test (<http://powerandsamplesize.com/Calculators/Compare-2-Means/2-Sample-Non-Inferiority-or-Superiority>). Allowing for 10% loss to follow-up yields a final sample size calculation of **57 per group for each of the three groups**.

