8.3 Statistical methods

The primary endpoint is change from baseline of the shoulder pain and disability index (SPADI). The low dose and high dose changes will be analyzed with a two-sided two-sample t-test. Noninferiority tests with a margin of .5 will be used to test for a clinically meaningful difference between 20mg and 40mg doses and the 40mg and 80mg doses. The three groups will be summarized with descriptive statistics and univariate statistical tests using analysis of variance for normally distributed continuous variables, Kruskal-Wallis test for non-normally distributed continuous variables, and the Fisher's exact test for categorical variables. The demographic data and SPADI data will be analyzed accordingly. All statistical analyses, graphics, and reports will be prepared following best practices in conducting reproducible research in statistics utilizing various software packages built around the R software platform. [name]., Associate Professor, will serve as the Biostatistician for this study.

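### SPADI change at three visits is primary with no deciding visit or success rule; the 2.5% level covers only the two dose pairs, the score is named inconsistently, and baseline SPADI is not used as a covariate

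*Combined protocol and SAP*

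**What the plan says.** - **Visits.** Section 1.2 lists as primary "Change in Overall SPADI scores at baseline compared to 2,4, and 6 months", with adverse reactions as a second primary item. Section 8.2 says "The primary endpoint is change in overall pain score on the SPADI at two, four, and six months from baseline". Section 8.3 restates the endpoint as SPADI change from baseline and gives no time.
- **Score.** Section 1.2 refers to the overall SPADI and 8.3 to the SPADI. Section 8.2 refers to a pain score and defines its three means to "be the average change in overall pain scale for the three different doses".
- **Level and size.** The 52 per group comes from an "80%-power 2.5%-level (since there are two tests) non-inferiority test". The two tests are 20 vs 40 mg and 40 vs 80 mg. The 20 vs 80 mg comparison has its own calculation: "This requires a sample size 51 per group based on a two-sided 80%-power 5%-level t-test".
- **Margin and SD.** Section 8.2: "Allowing for a non-inferiority margin of 15", with an SD of 20 for non-inferiority and 40 in the 20 vs 80 mg example. Section 8.3 gives the margin as .5, without a unit.
- **Analysis.** Section 8.3: "The low dose and high dose changes will be analyzed with a two-sided two-sample t-test". It adds ANOVA, Kruskal-Wallis and Fisher tests, but no repeated-measures or covariate-adjusted model.
- **Data available.** Under 7.2.2 the SPADI is completed after consent and before randomization. Under 7.2.3 it is repeated at 2, 4 and 6 months.
- **Expected time course.** Section 2.1 says that most patients are back at baseline 2 to 3 months after an injection.

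**The concern.** Three SPADI assessments are primary, and the plan does not say how they combine into one conclusion. The deciding analysis could therefore be picked after results are seen. The choice is not neutral: by section 2.1, the 2-month visit falls near the end of the usual benefit and the 4- and 6-month visits fall after it. If every arm has returned to baseline, dose differences shrink and non-inferiority becomes easier to show. Section 10.6 plans an interim look after 25% enrolment, so data may be seen while the choice is still open.

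The consequence depends on the rule. If any visit suffices, the error rate rises. If all must succeed, error is protected but power may be lost. With one named visit, neither happens. Because the score wording differs, it is also unclear which score the SD of 20 and the margin of 15 describe. Separately, a baseline measurement that could sharpen every contrast is used only to form the change score.

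**Working it through.** **Inputs from 8.2:** margin 15, SD 20, difference 4, one-sided 2.5%, 52 per group; for 20 vs 80 mg, d = .5 (difference 20, SD 40), two-sided 5%. The 4 is taken as an unfavourable deficit, which is what the 52 requires.

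**Assumed, because the documents give no values:** between-visit correlation ρ from .5 to .9, equal for all pairs of visits; baseline to follow-up correlation r of .3, .5 or .7, with equal SDs at baseline and follow-up.

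**1. The plan's figure.** n = 2 × [20 × (1.960 + 0.842)/(15 − 4)]² = 51.9, so 52. It reproduces for one comparison at one time. The two tests at 2.5% use the whole 5%, leaving nothing for three visits. The 20 vs 80 mg test lies outside that split.

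**2. All three visits required.** SE = 20 × √(2/52) = 3.922. A visit with a 4-point deficit has limit 11/3.922 − 1.960 = 0.844; a visit with none has 15/3.922 − 1.960 = 1.864. Power per dose pair is the trivariate normal probability that all three variables lie below their limits.

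| Deficit at 2/4/6 months | ρ = .5 | ρ = .7 | ρ = .9 |
|---|---|---|---|
| 4/4/4 | 61% | 66% | 72% |
| 4/4/0 | 68% | 71% | 75% |
| 4/0/0 | 78% | 79% | 80% |

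One visit alone: Φ(0.844) = 80%.

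**3. Any visit suffices.** The chance that at least one of three correlated two-sided 5% tests rejects, with no true 20 vs 80 mg difference, is 12.5% (ρ = .5), 10.9% (.7) and 8.4% (.9). The six non-inferiority tests (two pairs, three visits), with both pairs exactly at the margin throughout, give the same figures. At ρ = 0 the rate is 14.3%.

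**4. Three-visit mean.** The variance factor is (1 + 2ρ)/3, which is .667 to .933.
- Non-inferiority with a 4-point deficit throughout: power 93% to 83%.
- 20 vs 80 mg, a 20-point difference at 2 months only: the mean difference is 20/3 = 6.67, the SD is 40 × √factor = 32.7 to 38.6, and power at 52 per group is 18% to 14%. At the 2-month visit alone it is 71%.
- Non-inferiority with a 20-point deficit at 2 months only, which exceeds the margin there: the mean deficit is 6.67, and non-inferiority is declared with probability Φ[(15 − 6.67)/(3.922 × √factor) − 1.960] = 74% to 59%.

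**5. Baseline as covariate.** Variance relative to the change score is (1 + r)/2.

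| r | Variance ratio | 20 vs 80 mg, d = .5, n = 52 | Non-inferiority, n = 52 |
|---|---|---|---|
| unadjusted | 1 | 71% | 80% |
| .3 | .65 | 88% | 94% |
| .5 | .75 | 83% | 90% |
| .7 | .85 | 78% | 86% |

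**6. Dependence on the SD.** With SD 40, SE = 40 × √(2/52) = 7.845 and power at 52 is Φ(11/7.845 − 1.960) = 29%. The requirement would be 4 × 51.9 = 207.6, so 208 per group.

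**The case against.** The other side has several good points.

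- **A reader might infer that the trial's error rate is inflated.** The documents do not support that. The three times are joined by *and*, and no section lets one visit suffice. The 12.5% to 8.4% describes a reading that the plan fails to exclude, not one it adopts.
- **A reader might infer that 80% power is lost.** That needs both an all-visits rule, which is not stated, and a deficit lasting beyond 2 months. The 2-month-only pattern is closest to section 2.1, and there the loss is negligible (78% to 80%).
- **Averaging the visits looks like a free solution.** It is not. When the effect fades, the mean dilutes a real early difference and makes non-inferiority easier to declare. It also needs a rule for missed visits: section 3.3.2 ends data collection at withdrawal, and 8.3 has no missing-data method.
- **The score wording may look like three different names.** It is one conflict. Sections 1.2 and 8.3 agree with each other and with the pain-and-function aim of 1.1; only 8.2 speaks of pain.
- **The covariate is a matter of efficiency.** This is right: the t-test on change is valid under randomization. It remains worth raising because the gain needs no new data, though its size rests on assumed correlations.

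None of this supplies a primary visit, a summary or a success rule.

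**Conclusion.** The point stands: the primary analysis is not tied to a visit, and the 2.5% level does not address the three visits. This should be corrected, but it does not invalidate the design, because a single visit fits the 52 per group as calculated. Under an all-visits rule, non-inferiority power is 61% to 72%, 68% to 75%, or 78% to 80%, according to whether the deficit persists, lasts to 4 months, or is present at 2 months only. These figures rest on the assumed correlations of .5 to .9 and on the SD of 20 and margin of 15.

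Naming a visit does not by itself secure 52 per group. The margin is 15 in 8.2 and .5 in 8.3, and 8.2 uses SDs of both 40 and 20. That the stated 51 per group gives 71% rather than 80% two-sided power is a separate matter; here it only sets the starting value for the 20 vs 80 mg comparison.

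**What to change.** (a) In 8.3, estimate the 20 vs 80 mg contrast and both non-inferiority contrasts, with confidence intervals, from an ANCOVA with baseline SPADI as covariate.

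(b) In 1.2, 8.2 and 8.3, name one primary visit before any data are reviewed, including at the interim look in 10.6. Justify it against the time course in 2.1 and make the other visits secondary. If a summary such as the three-visit mean is preferred, state that it dilutes a fading effect and favours non-inferiority, and say how missed visits are handled.

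(c) Use one score name in all three sections. Confirm that the 15-point margin and the SD of 20 apply to that score, and reconcile them with the .5 in 8.3 and the SD of 40 in 8.2. If either does not hold, recalculate the sample size.

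**Cost:** wording in three sections and a little more programming, with no new data collection. Two visits now listed as primary become secondary. These changes do not settle how the separate 5% test for 20 vs 80 mg, or adverse reactions as a second primary item, fit into overall error control.

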1.0 Objectives

1.1 Study Objectives

The purpose of this study is to determine the most effective intraarticular steroid dose for the treatment of glenohumeral osteoarthritis. We aim to randomize patients into low, medium, and high dose groups of injectable corticosteroids as these doses are typically used in the standard of care for our patients. To date there has been no study to evaluate which dose is most efficient with the fewest side effects for glenohumeral osteoarthritis. Our objectives will be to provide ultrasound guided intraarticular glenohumeral injections of these randomized concentrations and to evaluate pain and function before and following injection with the Shoulder Pain and Disability Index (SPADI). We hypothesize that the low dose steroid will provide equivalent improvement of the pain and function to the medium and high doses, while minimizing side effects.

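### Section 1.1 hypothesises that 20mg is equivalent to both 40mg and 80mg, but 20mg vs 80mg is tested only for difference, with no margin, and no rule says how the three planned tests combine

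*Combined protocol and SAP*

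**What the plan says.** Section 1.1 (Study Objectives) sets the hypothesis: "We hypothesize that the low dose steroid will provide equivalent improvement of the pain and function to the medium and high doses". That is two comparisons, 20mg vs 40mg and 20mg vs 80mg.

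Section 8.2 (Sample size determination) plans a different set. It sizes 20mg vs 80mg to detect a difference and adds "conducting non-inferiority tests in the 20mg vs 40mg and 40mg vs 80mg groups". Section 8.3 (Statistical methods) repeats the pattern: "The low dose and high dose changes will be analyzed with a two-sided two-sample t-test", and "Noninferiority tests with a margin of .5 will be used to test for a clinically meaningful difference between 20mg and 40mg doses", followed by the same for 40mg vs 80mg. The other three-group tests in 8.3 (analysis of variance, Kruskal-Wallis, Fisher's exact) also test for difference and use no margin.

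A margin is therefore given for the adjacent doses only. In 8.2 it is "Allowing for a non-inferiority margin of 15 (so that differences less than 15 are deemed clinically non-inferior" (points); in 8.3 it is .5 with no unit. The only words that link any of the tests are in 8.2: "80%-power 2.5%-level (since there are two tests) non-inferiority test". On timing, 8.2 says "The primary endpoint is change in overall pain score on the SPADI at two, four, and six months from baseline" and does not say to which visit, or combination of visits, the tests apply.

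**The concern.** A hypothesis of equivalence needs each comparison it names to be judged against a margin. Here 20mg vs 40mg is, and 20mg vs 80mg is not. 40mg vs 80mg has a margin but is not part of the hypothesis.

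There are two tempting routes to a conclusion about 20mg vs 80mg, and neither is sound alone. A non-significant t-test may reflect only limited precision. Passing both adjacent tests allows two losses, each inside the margin, to add up to one outside it.

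The plan also does not say which pattern across the three tests would support the hypothesis and which would refute it. The reading could then be chosen after the results are seen. At stake is whether the trial, run exactly as planned, can support the low-dose vs high-dose half of its own hypothesis.

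**Working it through.** **Inputs from section 8.2.** 52 per group; margin 15; SD 20 in the non-inferiority calculation and SD 40 in the 20mg vs 80mg calculation ("differences of 40 vs 20 with a standard deviation of 40"); steps of 4 between adjacent doses, so 8 between 20mg and 80mg; 2.5% per non-inferiority test, taken as one-sided.

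**My assumptions.** One time point, normal approximation, lower dose worse in equal steps. Joint probabilities are simulated (2,000,000 to 4,000,000 trials).

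**1. The plan's own figure.** n = 2 × [(1.960 + 0.842) × 20 / (15 − 4)]² = 51.9, so 52 per group, as stated. This works only if the 4-point step runs against the lower dose. The means as listed for low, medium and high (40, 36, 32) run the other way if a larger change is better, and would give 2 × [2.802 × 20 / 19]² = 17.4, so 18.

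**2. What two adjacent passes imply.** If 80mg exceeds 40mg by less than 15, and 40mg exceeds 20mg by less than 15, then 80mg exceeds 20mg by less than 30. That is twice the difference 8.2 accepts.

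**3. Precision.** SE = SD × √(2/52) = 3.92 at SD 20 and 7.84 at SD 40. The 95% half-widths are 7.69 and 15.38.

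**4. The t-test alone, true 15-point loss on 20mg.** Chance of a non-significant result ≈ Φ(1.960 − 15/SE):
- SD 40: Φ(0.05) = 52%
- SD 20: Φ(−1.87) = 3%

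**5. The adjacent pair alone, true 15-point loss (7.5 per step), SD 20.** Each test passes with probability Φ(7.5/3.92 − 1.960) = Φ(−0.05) = 48%. The two contrasts share the 40mg arm (correlation −0.5), and both pass in 14.8% of trials. A direct 20mg vs 80mg test at margin 15 passes in 2.5%. At SD 40 the pair passes in only 0.4%. The weak routes in steps 4 and 5 arise under different SDs and must not be added.

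**6. All three tests read together.** Suppose the claim also required that the t-test not show 20mg worse. At SD 20 that removes 12.4 of the 14.8 percentage points and leaves 2.4%. By SD, at a true 15-point loss:

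| SD | 18 | 20 | 22 | 24 | 26 | 30 | 40 |
|---|---|---|---|---|---|---|---|
| False claim | 1.0% | 2.4% | 3.9% | 4.6% | 3.8% | 1.7% | 0.4% |

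**7. Power of a direct claim** (20 vs 40 and 20 vs 80 both meet margin 15 at one-sided 2.5%, 52 per group). For 20 vs 80 alone, power = Φ((15 − loss)/SE − 1.960). The joint figure allows for the shared 20mg arm (correlation 0.5).

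| True 20 vs 80 loss | SD | 20 vs 80 alone | Both |
|---|---|---|---|
| 0 | 20 | 97% | 94% |
| 0 | 40 | 48% | 31% |
| 8 | 20 | 43% | 40% |
| 8 | 40 | 14% | 9% |

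If the .5 in 8.3 means SD units (an assumption), then margin/SE = 0.5/√(2/52) = 2.55 whatever the SD. With equal doses, power is Φ(2.55 − 1.96) = 72% for 20 vs 80 alone and about 58% for both.

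**The case against.** The best defence is that the three planned tests, read together, already control the error well. Step 6 bears this out: at most about 4.6%, and 2.4% at the plan's SD of 20. That stands, and it narrows the harm. But the combined reading appears nowhere in the plan. The 2.5% in 8.2 sets the level for sizing two tests; it leaves out the 5% t-test and is not a decision rule.

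A second defence is that section 1.1 also aims to find the most effective dose, and a difference test between the extreme doses serves that aim. This is fair, and it is why rewording the hypothesis is an acceptable remedy. It does not make the t-test a test of equivalence.

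Third, with the means as listed in 8.2 the low dose is best and no loss scenario arises. True, but the same sentence gives differences of the opposite sign, and only those reproduce 52. The mismatch between 1.1 and 8.2/8.3 does not depend on the direction.

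A reader might infer something stronger: that the planned tests will often contradict each other. At SD 20, margin 15 and 4-point steps against the lower dose, 21.8% of trials pass both adjacent tests while the t-test shows 20mg worse than 80mg. The documents do not support a general statement of that kind. The figure is 0.0% at SD 40, and 0.0% if .5 means SD units. Nor is it an error rate: an 8-point loss lies inside the margin of 15, so both findings would be true.

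Nor should a reader infer that a direct test abolishes such overlap. At an 8-point loss the overlap is nil with 52 per group and SD 20. It is about 3% with 57 per group, and with 52 per group it is 11.9% at SD 18 and 31.9% at SD 16.

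**Conclusion.** The point holds and should be fixed before the data are analysed. As written, the plan has no test that could support equivalence of 20mg to 80mg, and it has no rule for combining the three tests it does plan.

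The size depends on inputs the plan leaves unsettled. At a true 15-point loss with 52 per group, relying on the t-test alone would miss the loss in 52% of trials (SD 40) or 3% (SD 20). Relying on the adjacent pair alone would pass 20mg in about 15% (SD 20) or 0.4% (SD 40), against 2.5% for a direct test. These figures assume one time point, margin 15, equal steps and the lower dose worse.

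The documents do not support saying that the planned tests, read jointly, have a badly inflated error rate. The defect is the mismatch with section 1.1 and the missing rule.

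**What to change.** First reconcile the margin (15 in 8.2, .5 in 8.3), the SD (20 and 40 in 8.2) and the direction of the assumed means. Then, in 8.3, with 8.2 to match:

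- Report the 20mg vs 80mg difference with its 95% confidence interval, which also gives the planned t-test, and judge it against the pre-specified margin.
- Claim that the low dose is as good as both higher doses only if 20 vs 40 and 20 vs 80 both meet the margin at one-sided 2.5%. The 40 vs 80 test can stay as planned.
- State that a non-significant t-test is not evidence of equivalence.
- State that if the margin is met while the interval excludes zero against 20mg, the conclusion is that 20mg is within the margin but measurably worse, with the interval reported.
- Name the time point, or the rule across 2, 4 and 6 months. Requiring both tests to pass at all three visits would cut joint power (SD 20, margin 15) to 12–29% at an 8-point loss and 86–91% if the doses are equal, assuming between-visit correlations of 0.3 to 0.9.

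If the sponsor does not want this claim, restate the hypothesis in 1.1 to match the planned tests.

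The cost is no new patients, visits or data, but the power in step 7 must be stated and may be low: at SD 40 the claim would fail about two times in three even if the doses were equal. For scale, 80% power for 20 vs 80 at an 8-point loss and SD 20 would need 2 × [2.802 × 20 / 7]² = 128.2, so 129 per group. Enrolling more is not proposed; the limit should be stated.
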